#### 6.0 STUDY DESIGN AND DESCRIPTION

# 6.1 Study Design

This is a phase 3, randomized, double-blind, parallel-group, placebo-controlled study in subjects with CIC as determined by the Rome III Diagnostic Criteria for Functional Constipation [4]. This study consists of a 14-day Screening Period and a subsequent 4-week (28 days) Double-Blind Treatment Period in which subjects will receive either lubiprostone or matching placebo BID. Subjects will be randomized to either active lubiprostone or placebo in a 1:1 ratio.

During the Screening Period, the defecation behavior of each subject is recorded in a diary to confirm he/she has constipation. Use of all existing laxatives is stopped at the beginning of the Screening Period (Visit 1). Subjects are instructed not to change their diet or lifestyle habits during the study. A total of 10 mg of bisacodyl suppository (or any equivalent drug) may be prescribed as a standard rescue medication if a subject has no adequate bowel movement for 3 consecutive days during the Screening Period of the study. When bisacodyl suppository does not improve constipation, glycerin enema (or equivalent drug) will be given. Subjects are instructed to complete their diaries before using rescue medications.

The subject diary will be distributed on Study Days -15, -1, 8 and 15. Subjects will be instructed to keep the diary every day including on the morning of Visit 1.

If the rescue medications fail to improve constipation, the investigator may decide to use another rescue medication. The recommendation may include a medication from the excluded medication list other than any form of polyethylene glycol (PEG), linaclotide, methylnaltrexone, or prucalopride, all of which are considered prohibited rescue medications. No rescue medication may be given 24 hours prior to and until 48 hours after the first dose of the study drug (Day 1). Subjects who use a rescue medication within 24 hours before the first dose of study drug on Day 1 should be withdrawn from the study. Those who use a rescue medication within 48 hours after dosing on Day 1 will be discontinued from the study by the investigator. The dose and mode of administration of rescue medications must be recorded in the electronic case report form (eCRF).

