## 13.1.3 Efficacy Analysis

Two-sided tests at a significance level of  $\alpha$ =5% will be used throughout unless otherwise stated. The null hypothesis is that lubiprostone is equal to placebo against the alternative that lubiprostone is different to placebo. All analyses will be performed using the FAS. Analyses specified for the PP are to be regarded as supportive evidence. There will be no adjustment for multiplicity.

All efficacy endpoints will be summarized by treatment and visit. If baseline measures are also defined and collected for an efficacy endpoint then change from Baseline at each visit will also be presented by summary statistics by treatment and visit. Baseline is defined as the last recorded measurement prior to treatment. For parameters based on diary data, baseline values will be derived using the data from the Screening Period.

Centers may be pooled geographically if necessary for analysis purposes.

The LOCF technique will be used to impute missing values. For a given subject, the most recent nonmissing treatment-period data point will be carried forward to the subsequent week where data are missing. Supportive analyses will be conducted without missing value imputation (ie, without LOCF) and with a 'worse-case' scenario where missing values are assigned the worst case values recorded in the study by any subject for that endpoint at that time.

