# 6.0 DETERMINATION OF SAMPLE SIZE

Assuming equal allocation, a power of 90%, an alpha level of 0.05 for a 2-sided test, a placebo mean of 4 (standard deviation of 2.7), and a treatment mean of 5.9 (standard deviation of 4) for SBM frequency at Week 1 and using the Wilcoxon-Mann-Whitney test [1], a total sample size of 146 is required. The Wilcoxon-Mann-Whitney test is a non-parametric test of the null hypothesis that the distribution is the same for both placebo and treatment responses against the alternative that there is a location difference between the two. The primary analysis will be conducted using the van Elteren test, which is a stratified version of the Wilcoxon-Mann-Whitney test, use of the Wilcoxon-Mann-Whitney test for sample size estimation will provide an approximate sample size for the van Elteren analysis. The estimates of placebo and treatment response are based on a previous study conducted by Sucampo Pharmaceuticals in the United States of America (Protocol No. RTU/0211SC0131).

The primary endpoint requires subjects to complete at least 4 days of the study diary, therefore assuming a non-evaluable rate of 3% by Day 4 an additional 4 subjects are required, giving a total of 150 subjects.

1 5

	CROSS-REGIONAL TEMP	LATE	
Template Number:	C-TMPL-DO-801	Page:	12 of 31
Version Number:	1.2	Effective Date:	14 Sep 201
This version replaces	s: 1.1		
Parent Document:	C-SOP-DO-800		
Template Title:	Statistical Analysis Plan (Legacy Takeda)	)	

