As the primary endpoint is within the first week of study treatment and only 4 days of diary collection are required it is not anticipated that missing values should be a cause of concern therefore the LOCF technique will be used to impute missing values for efficacy analysis purposes only. For a given subject, the most recent nonmissing data point will be carried forward to the subsequent week where data are missing. Details for each efficacy parameter are given below. It is expected, based on previous studies, that the number of subjects with in-sufficient post baseline data for the primary endpoint will be small therefore a simple approach to handling missing data will be used. Where there is no post baseline efficacy data then the baseline value will be used, it is expected that the number of SBMs should increase for those on treatment, therefore using a baseline value for missing post baseline data assumes no treatment effect, this approach can be considered conservative,. To examine the effect of the requirement to have at least a minimum of 4 days post baseline efficacy data for the primary endpoint, using the stratified van Elteren test [2], will be conducted using all valid SBM data post baseline even when less than 4 days data is present, only where there is no post baseline data will baseline be used in this analysis.

An SBM is defined as any BM that does not occur within 24 hours after rescue medication use. Certain periods after taking rescue medication will be defined as "blackout periods" during which BMs are considered as non-spontaneous. Blackout periods, including those with missing or partial times for rescue medication use in the diary, will be handled as follows:

0-24 hours post rescue medication intake if the time is fully specified.

0-24 hours post rescue medication intake if the hour is present, but the minute is missing. The blackout time will commence from the imputed time. If the minutes are incomplete or missing from either the rescue medication or bowel movement entry then it is assumed that the missing values are zero and an imputed time will be calculated. e.g.

1	5	_	_	=	1	5	0	0
2	1	5		=	2	1	5	0

0-48 hours, beginning from midnight on the day the rescue medication intake is recorded for, if the hour is missing from the time entry for the rescue medication.

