7.8.1 Primary Efficacy Endpoint(s)

The primary efficacy endpoint is SBM frequency at Week 1; an SBM is defined as any BM that does not occur within 24 hours after rescue medication use. Since rescue medication use will be disallowed during Week 1, the SBM frequency should equal the BM frequency. In the case of protocol violators, the analysis will be based on SBMs.

In order to adjust for early withdrawals or those with less than 7 days diary data, weekly SBM frequency will be calculated as follows:

7 x (Number of SBMs / Number of days)

Where the number of days is the number of days during the week that the subject was in the study. Weeks will be calculated as 168-hour intervals starting from the day after randomization (Day1), if there is no time recorded for the morning dose on Day1 then the time of the first recorded morning dose will be used. The number of days will generally be 7 unless a subject drops out during a treatment week. If the number of days is less than 4, then the data will be considered insufficient and the frequency will be missing.

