## Primary Analysis

Since outliers are commonly observed in these data, parametric models may not be robust. The efficacy data will therefore be analyzed by a van Elteren test stratified by center. If necessary, small centers will be pooled as mentioned above. This procedure will test the null hypothesis of equal SBM rates between treatments at the end of Week 1 versus the alternative hypothesis of non-equality between the 2 groups; the test will be conducted at a 2-sided significance level of 0.05. A related 95% confidence interval and point estimate will be provided for the treatment difference; the confidence interval will be estimated by inverting the hypothesis test. This endpoint will be analyzed for the FAS.

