# Sensitivity Analyses

The primary analysis as described above will be repeated using the PP rather than the FAS. An additional sensitivity analysis using the FAS assuming a 'worse-case' scenario approach will also be conducted, where missing values, including those with < 4 days diary data, are assigned the worst case values (the lowest SBM frequency for week 1) recorded in the study by any subject for that endpoint at that time.

Additionally the endpoint will be analyzed using robust analysis of variance (ANOVA) models (by M-estimation [3] using PROC ROBUSTREG in SAS) with center and treatment in the model as a sensitivity analysis using the FAS. The interaction between treatment and center will also be examined in a separate model, using robust ANOVA methods as previously described.

To examine the effects of any permanent dose reduction in response to an AE (as recorded on the eCRF) an additional sensitivity analysis will also be performed. This will be performed on the

CROSS-REGIONAL TEMPLATE			
Template Number:	C-TMPL-DO-801	Page:	22 of 31
Version Number:	1.2	Effective Date:	14 Sep 2015
This version replaces:	1.1		
Parent Document:	C-SOP-DO-800		
Template Title: St	tatistical Analysis Plan (Legacy Takeda)		

FAS where data from those subjects with a dose reduction will be excluded from the time of dose reduction (taken as date of last BID dose + 12 hours, e.g. if the evening dose is removed then the time will be from the morning dose + 12 hours, if the morning dose is removed then it will be from the previous day's evening dose + 12 hours) and subjects will be treated as a dropout from this time point onwards. This will be implemented using robust ANOVA. Additionally, another factor will be added to the robust ANOVA model to examine the effect of dose reduction (), this will be performed on the FAS. This analysis will not be carried out if the number of subjects with a dose reduction within the first week is less than 5%.

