#### 7.8.2 Secondary Efficacy Endpoint(s)

The interaction of treatment and center and the effect of dose reduction will not be examined for any secondary endpoints. All secondary endpoints will be analyzed for the FAS only.

SBM frequency at Week 2, 3 and 4

The secondary endpoint will be analyzed as specified for the primary endpoint separately for each week.

Additionally for patients with a missing Week 2 frequency estimate (where diary days < 4 in Week 2) the Week 1 estimate will be carried forward, if available. For the worse-case analysis all missing Week 2 values will be assigned the lowest SBM frequency for week 2.

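### The 'worse-case' analysis is worst for the subject, not for the treatment comparison: if placebo loses clearly more subjects, it flatters lubiprostone

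*SAP*

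**What the plan says.** SAP 7.8.1 (Sensitivity Analyses) plans a 'worse-case' run on the FAS. Missing Week 1 values, including those from subjects with fewer than 4 diary days, "are assigned the worst case values (the lowest SBM frequency for week 1) recorded in the study by any subject". Protocol 13.1.3 has the same rule in general form: "missing values are assigned the worst case values recorded in the study by any subject for that endpoint at that time". SAP 7.8.2 restates it for the next week: "For the worse-case analysis all missing Week 2 values will be assigned the lowest SBM frequency for week 2". Weeks 3 and 4 follow because they are to be analysed like the primary endpoint. None of these places separates the arms.

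Three other provisions matter here.
- A Week 1 value is missing under SAP 7.8.1 as follows: "If the number of days is less than 4, then the data will be considered insufficient and the frequency will be missing".
- The SAP's primary handling is in 7.8: "Where there is no post baseline efficacy data then the baseline value will be used". The SAP calls this conservative.
- Protocol 6.1 provides one route to early loss: "Those who use a rescue medication within 48 hours after dosing on Day 1 will be discontinued from the study by the investigator".

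The primary test is in SAP 7.8.1: "The efficacy data will therefore be analyzed by a van Elteren test stratified by center".

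**The concern.** Giving every missing subject the lowest frequency pulls both arms down. A missing lubiprostone subject then counts against the drug, but a missing placebo subject counts for it. Which effect wins depends on how many subjects each arm loses, so the run does not bound the treatment difference from below.

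The baseline fill in the primary analysis leans the same way. Protocol Table 4.a shows baseline means of 1.28 to 1.68 SBMs per week, against placebo Week 1 means of 2.93 to 3.99, so baseline fill also lowers missing placebo subjects. Agreement between the primary and 'worse-case' results is therefore weak evidence of robustness if placebo loses more subjects. No planned analysis fills the arms in opposite directions or looks for the point at which the conclusion changes.

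At stake is how a 'worse-case' p-value is read. If it is smaller than the primary one, it could be taken as proof of robustness when it partly reflects which arm lost subjects.

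**Working it through.** **Inputs.** From SAP 6.0: placebo mean 4 (SD 2.7), lubiprostone mean 5.9 (SD 4), "a power of 90%, an alpha level of 0.05 for a 2-sided test", and 3% non-evaluable. From SAP 4.2: 75 per arm. From the Protocol study summary: about 10 sites.

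Assumed, because the documents do not give it:
- negative binomial counts with these means and SDs, lowest value 0;
- baseline averaging about 1.35;
- subjects missing at random within arm;
- 10 centers of 15;
- every missing Week 1 rate takes the baseline value in the primary analysis;
- the split of losses by arm.

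**Plan's own figure.** Pooled SD = √((2.7² + 4²)/2) = 3.41. The t-test needs 69 per arm. Dividing by the Wilcoxon efficiency 3/π gives 72.3, so 73 per arm and 146 in total, as stated. The planned loss is 0.03 × 150 = 4.5 subjects.

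**Rank-scale effect.** Let θ be the chance that a lubiprostone subject has more SBMs than a placebo subject, with ties counted half. Without missing data θ = 0.6421. An observed lubiprostone subject beats the lowest value with probability A = 0.9839. The lowest value beats an observed placebo subject with probability B = 0.0270. With missing fractions p (placebo) and l (lubiprostone), the lowest-in-both rule gives

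θ′ = (1−p)(1−l)θ + p(1−l)A + (1−p)l·B + p·l/2.

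- 4 placebo / 0 lubiprostone: (71/75)(0.6421) + (4/75)(0.9839) = 0.660, stronger than 0.642.
- 4/3: 0.5836 + 0.0504 + 0.0010 + 0.0011 = 0.636, weaker.

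**Threshold.** For small losses, θ′ exceeds the complete-case θ when p/l > (θ − B)/(A − θ) = 0.6151/0.3418 = 1.80. For the comparison with baseline fill, lubiprostone beats a baseline value with probability 0.9012, and a baseline value beats placebo with probability 0.1651. The threshold is then (0.1651 − 0.0270)/(0.9839 − 0.9012) = 1.67. A normal model gives θ = 0.653 and a complete-case threshold of about 1.9. On the mean scale the complete-case threshold is 5.9/4 = 1.48. Against baseline fill with equal baselines, any placebo excess is enough on that scale.

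| Missing P/L | θ complete case | baseline fill | lowest in both | opposite directions |
|---|---|---|---|---|
| 4/0 | 0.642 | 0.656 | 0.660 | 0.608 |
| 4/1 | 0.642 | 0.650 | 0.652 | 0.600 |
| 4/2 | 0.642 | 0.643 | 0.644 | 0.592 |
| 3/2 | 0.642 | 0.640 | 0.640 | 0.601 |
| 4/3 | 0.642 | 0.637 | 0.636 | 0.585 |
| 0/4 | 0.642 | 0.617 | 0.609 | 0.609 |

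'Opposite directions' gives missing lubiprostone subjects the lowest value and missing placebo subjects the highest.

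**Simulated van Elteren test**, 1,500 trials per row, mean Z (share above 1.96 in brackets):

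| Missing P/L | complete case | baseline fill | lowest in both | opposite directions |
|---|---|---|---|---|
| 4/0 | 2.89 (84%) | 3.22 (91%) | 3.31 (93%) | 2.23 (61%) |
| 4/1 | 2.93 (85%) | 3.14 (89%) | 3.19 (91%) | 2.12 (57%) |
| 2/2 | 2.89 (84%) | 2.81 (83%) | 2.79 (82%) | 2.25 (63%) |
| 8/6 | 2.79 (81%) | 2.74 (81%) | 2.70 (81%) | 0.62 (5%) |
| 0/4 | 2.91 (84%) | 2.42 (70%) | 2.27 (64%) | 2.27 (64%) |

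A separate simulation of the 4/0 row gave 3.00, 3.32, 3.42 and 2.32, the same pattern within simulation error.

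**Changing who is missing.** If the 4 missing placebo subjects are those with the lowest counts, the lowest-in-both rule gives a mean Z of 3.05, against 3.04 with full data. It then recovers the truth.

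**The case against.** **The definition.** Both documents define the worst case as the worst recorded value for the endpoint, and neither claims it is the worst treatment contrast. That is correct. The complaint is about the label and what the run can show, not about a breach of the plan.

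**Size and mechanism.** The planned loss is 4 to 5 subjects, and even at 4/0 the shift against the primary analysis is only 3.31 − 3.22 = 0.09 in Z. No document gives losses by arm. The rescue rule removes only subjects who take rescue while it is barred, and those subjects plausibly do have low counts. Losses to adverse events (Protocol 7.5 and 7.7) could fall more on lubiprostone. All of this stands and limits the point.

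**Other checks.** Protocol 13.1.3 also plans an analysis without imputation, and SAP 7.8 adds one using all valid Week 1 data from subjects with under 4 days. These help. However, SAP 7.8 and 7.8.1 do not list the analysis without imputation for the primary endpoint, and the under-4-day analysis still falls back on baseline where there are no data. The per-protocol run changes which subjects are included and adds no adverse fill.

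**Stronger readings that the documents do not support.**
- A reader might infer that the run helps lubiprostone whenever placebo loses more. On the planned rank test it does not: 4/3 and 8/6 weaken the effect.
- A reader might infer that it can never count against the drug. At 0/4 it equals the opposite-direction worst case.
- A reader might infer inflated false-positive error. That requires forcing a lopsided split while assuming no drug effect, yet the reason for expecting more early rescue on placebo is that the drug works. With equal random loss and no effect, the simulated one-sided rate is 2.5% at 3% loss and 2.4% at 7%.

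**Conclusion.** The point holds in limited form. The planned run is the worst outcome for each missing subject and not a worst case for the comparison. It is conservative with similar or lubiprostone-heavy losses. It overstates the effect relative to complete cases, and slightly relative to the primary analysis, when placebo losses are about 1.7 to 1.8 times lubiprostone losses or more.

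The largest case near the planned loss, 4/0, moves θ from 0.642 to 0.660, while filling in opposite directions gives 0.608. These figures depend on the assumed count distribution, baseline and loss split, and on data missing at random within arm. The excess largely vanishes if the missing placebo subjects truly have low counts. This is an inexpensive improvement to the robustness evidence, not a flaw in the primary analysis.

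**What to change.** In SAP 7.8.1, and in 7.8.2 for Weeks 2 to 4, keep the present run but rename it 'lowest value in both arms'.

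Add one tipping-point analysis on the FAS with the same van Elteren test:
- set missing lubiprostone values to the lowest observed frequency for that week;
- raise missing placebo values stepwise from the lowest value, through the observed lubiprostone median, to the observed maximum;
- report where p first exceeds 0.05, or that it never does.

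Make the change before unblinding. The cost is SAP wording and one more run of the same program. The far end is pessimistic: with the lowest-count placebo subjects missing at 4/0, the placebo maximum gave a mean Z of 1.92 against 3.02 with full data. Present that end as a bound and not as the expected result.

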#### **Secondary Objectives:**

None

Subject Population: Male and nonpregnant, nonlactating female subjects 19 years of age and older with CIC.

Number of Subjects:	Number of Sites:	
Lubiprostone 24 µg group: Approximately 75 randomized	Estimated total: Approximately 10 sites in Korea	
Placebo group: Approximately 75 randomized		
Estimated total: Approximately 150 randomized		

Dose Level(s):	Route of Administration:
24 μg lubiprostone capsule or matching placebo taken BID	Oral
Duration of Treatment:	Period of Evaluation:
BID for 4 weeks	Up to 56 days

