# 13.1.3.1 Primary Endpoint

The primary endpoint for the study is the frequency of SBM at Week 1. An SBM is defined as any BM that does not occur within 24 hours after rescue medication use. The SAP will contain more details on the handling of rescue medication and missing or partial data.

In order to adjust for early withdrawals, weekly SBM frequency rates will be calculated as follows:

(Number of SBMs / Number of Days) 
$$\times$$
 7

The number of days in the denominator above is the number of days during the week that the subject was in the study. Weeks will be calculated as 168-hour intervals starting with the exact time of the first intake of study drug. The number of days will generally be 7 unless a subject drops out during a treatment week. If the number of days is less than 4, then the data will be considered insufficient and the rate will be set to missing.

The primary endpoint will be analyzed using van Elteren's test stratified by center to examine the difference between lubiprostone and placebo. Additionally the endpoint will be analyzed using analysis of variance (ANOVA) models with center and treatment in the model as a sensitivity analysis. The estimated least squares (LS) means, related mean difference and associated 95% CI will also be presented to aid interpretation of the clinical effect. The interaction between treatment and center will also be examined in a separate ANOVA model.

This endpoint will be analyzed for the FAS. A sensitivity analysis using the PP will also be presented.

To examine the effects of any dose reduction in response to an AE an additional sensitivity analysis will also be performed. This will be performed on the FAS where data from those subjects with a dose reduction will be excluded from the time of dose reduction and subjects will be treated as a drop-out from this time point onwards. Additionally, another factor will be added to the ANOVA model to examine the effect of dose reduction, this will be performed on the FAS, with no subjects excluded.

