# 7.8 EFFICACY ANALYSIS

The primary and secondary endpoints will be derived from the daily diary data entered by patients.

Two-sided tests at a significance level of  $\alpha$ =5% will be used throughout unless otherwise stated. The null hypothesis is that lubiprostone is equal to placebo against the alternative that lubiprostone is different to placebo. All analyses will be performed using the FAS. Analyses specified for the PP are to be regarded as supportive evidence. There will be no adjustment for multiplicity.

All efficacy endpoints will be summarized by treatment and visit. If baseline measures are also defined and collected for an efficacy endpoint then change from Baseline at each visit will also be presented by summary statistics by treatment and visit. Change from baseline will be calculated as (post-baseline value) – (baseline value). Baseline is defined as the last recorded measurement prior to treatment.

For diary data, baseline values will be the average of all diary data from the screening period (Days -14 through -1, inclusive, relative to day of first dose). If more than 14 days of diary data are collected during the screening period only the data from Day -14 onwards will be used. If fewer than 8 days are available then the baseline value will be set to missing.

Centers may be pooled geographically if necessary for analysis purposes. This will be determined before database lock.

CROSS-REGIONAL TEMPLATE				
Template Number:	C-TMPL-DO-801	Page:	20 of 31	
Version Number:	1.2	Effective Date:	14 Sep 2015	
This version replaces:	1.1			
Parent Document:	C-SOP-DO-800			
Template Title: S	statistical Analysis Plan (Legacy Takeda)			

For weekly SBM frequency, at least 4 days of diary data are required to compute a weekly estimate, if there are less than 4 days recorded in a week then the SBM frequency for that week will be set to missing.

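### The treatment-by-centre interaction test in SAP 7.8.1 (M-estimation) does not hold the stated 5% level with about 10 unpooled centres; the protocol's ANOVA F-test does, or nearly so

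*SAP*

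**What the plan says.** Protocol 13.1.3.1 plans, for the primary endpoint: "The interaction between treatment and center will also be examined in a separate ANOVA model".

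SAP 7.8.1, under Sensitivity Analyses, fits the treatment-plus-centre model "by M-estimation [3] using PROC ROBUSTREG in SAS) with center and treatment in the model as a sensitivity analysis using the FAS" and then states: "The interaction between treatment and center will also be examined in a separate model, using robust ANOVA methods as previously described". It does not name the weight function, the residual scale, the covariance estimate or the test statistic for the interaction.

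SAP 7.8 sets the two-sided level: "5% will be used throughout unless otherwise stated". No other level is given for the interaction. SAP 7.1 has any p-value at or below 0.05 reported as significant.

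Protocol 2.0 gives the number of centres as "Approximately 10 sites in Korea". SAP 7.8 allows pooling: "Centers may be pooled geographically if necessary for analysis purposes. This will be determined before database lock". Neither document gives a minimum centre size or a pooling rule.

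SAP 7.13 says only that the SAP adds detail and further analyses. It does not list the change of interaction method.

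**The concern.** Tests from an M-estimation fit rely on large-sample theory. With 10 centres and two arms the interaction model spends 20 parameters on about 150 subjects, or 7 to 8 per cell. The usual residual scale is a median of absolute residuals with no correction for fitted parameters, and one pooled scale serves both arms although their planned SDs differ (2.7 and 4). Each of these features can make the p-value too small. The least-squares F-test has an exact small-sample reference under normal errors and is usually robust to moderate departures.

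This interaction model is the plan's only formal check that the primary effect is consistent across centres. A false signal would be labelled significant under the SAP's own rule and would have to be explained in a study meant to support registration.

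**Working it through.** **Inputs.** Placebo mean 4 (SD 2.7), lubiprostone mean 5.9 (SD 4), total 146 rising to 150 (Protocol 13.3, SAP 6.0). About 10 sites (Protocol 2.0). Allocation 1:1. Two-sided 5% level (SAP 7.8). SAP 7.8.1 expects outliers, so skewed distributions are reasonable to simulate.

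**The plan's own figure.** The documents give no operating characteristic for the interaction test beyond the 5% level. The sample size does reproduce:
- Average SD = √((2.7² + 4²)/2) = √11.645 = 3.41.
- The t-test needs 69 per arm. Dividing by the Wilcoxon efficiency, 69/0.955 = 72.3, rounded up to 73, so 146 in total.
- 3% of 146 is 4.4; the plan adds 4 to reach 150.

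**Size of the model.** 1 intercept + 9 centre + 1 treatment + 9 interaction terms = 20 parameters. That leaves 150 − 20 = 130 residual degrees of freedom (126 with 146 subjects). The interaction has 9 df.

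**Simulation.** Each arm has the same distribution in every centre, so every rejection is false. The M-estimate used bisquare weights (c = 4.685) and the median residual scale. The 9-df interaction was tested by a Wald chi-square and a rho-type chi-square, next to the ordinary ANOVA F-test on the same data. At N = 150 the three layouts are equal centres, unequal centres, and unequal centres with arm imbalance within centre. Monte Carlo standard error near 13% is √(0.13 × 0.87/5000) = 0.5 points for 5,000 runs and 0.8 points for 2,000.

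Rejection at nominal 5%, 10 unpooled centres:

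| Data | Wald | Rho-type | ANOVA F |
|---|---|---|---|
| Planning values, skewed counts or normal, N=146 (2,000 runs) | 11.7-15.2% | 18.9-23.8% | 4.9-6.7% |
| Planning values, N=146 (1,000 runs) | 12-13% | 17-19% | about 5% |
| Negative binomial, planning values, N=150 (5,000 runs) | 13.0-15.2% | 18.3-21.4% | 5.4-5.7% |
| Gamma, planning values, N=150 (5,000 runs) | 14.1-16.6% | 19.0-21.4% | 4.8-6.4% |
| Lognormal, planning values, N=150 (5,000 runs) | 15.1-20.5% | 17.8-21.9% | 4.7-6.7% |
| Negative binomial, Japanese study values (Protocol Table 4.a), N=150 (5,000 runs) | 12.5-13.9% | 20.8-23.8% | 5.1-5.4% |

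The central Wald range is thus about 12-15%. It rises to 20.5% only with lognormal data and arm imbalance within centres.

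**What drives it.** At N = 150 with normal data (2,000 runs), the Wald rate is about 7% with equal variances and about 12% with the planned unequal SDs, so the unequal SDs add about 5 points. Symmetric heavy-tailed data (t with 3 df) give 7-11%. The rho-type test rejects 13-15%, 19-21% and 16-18% in those three cases.

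**Does the choice of settings rescue it?** With Huber weights (c = 1.345) the Wald rate is 10.5-18.0% and the rho-type rate 17.9-24.2%. An F reference for the bisquare Wald test still gives 11.0-18.8%.

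**Effect of pooling.** With 5-6 centres and the planning distributions, Wald falls to about 8-10% and rho-type to 9-13%. The F-test at 6 centres gives 4.5-5.4%.

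**F-test on ranks.** With 10 centres and no centre effects it rejects 4.5-5.8%. With assumed centre differences of SD 1 SBM per week it rejects 5.2-6.8%. With a large assumed centre SD of 3 it reaches 8.4% (10 centres) and 7.5% (6 centres), while the F-test on raw values stays at 5-6% when centre effects are added.

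**The case against.** The strongest reply has four parts.

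- **The rate is conditional.** It needs about 10 unpooled centres, settings that the SAP leaves open, and skewed or unequal-variance data. The upper end belongs only to the rho-type test, which the SAP does not name. Pooling is provided for and will be settled before database lock, and the number of sites is an estimate. This stands: a reader might take 12-24% as a fixed property of the SAP, and the documents do not support that. Against it, the planning SDs are themselves unequal, the SAP itself expects outliers, and pooling is only to happen if necessary.
- **The consequence is limited.** A reader might infer that the trial is likely to report false heterogeneity, or that the primary result is at risk. Neither follows. At 12-24% the trial is still 76-88% likely not to report a false interaction. The check sits among the sensitivity analyses with no decision rule attached, and it cannot alter the van Elteren p-value or its confidence interval.
- **The SAP had a reason.** It doubts parametric models because outliers are common, and SAP 7.1 allows alternative methods before unblinding if the reasons are documented. That supports a robust estimate of the treatment effect. It does not make the small-sample interaction test valid.
- **Ranks are not a perfect cure.** Ranking changes the interaction hypothesis, and the rank test drifts above 5% when centre differences are large. This also stands, so the rank test is better as a check than as the main interaction test.

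**Conclusion.** The point holds in a conditional form and is minor. With about 10 unpooled centres, the planned unequal SDs, bisquare weights, a median-based scale and a chi-square reference, the interaction test has a false-positive rate of about 12-15% (Wald) or 17-24% (rho-type), against about 5-7% for the protocol's F-test. That is roughly 2.4 to 4.8 times the nominal 5% (12/5 and 24/5). Pooling to about 6 centres brings it to about 8-13%; equal-variance normal data bring the Wald rate to about 7%. The type I error of the primary analysis is unchanged. The ROBUSTREG settings, the data distributions and the centre sizes are assumptions, because the documents do not give them.

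**What to change.** In SAP 7.8.1, replace the interaction sentence with one stating that treatment-by-centre interaction for Week 1 SBM frequency will be tested by the F-test from the separate ANOVA model of Protocol 13.1.3.1. Add the same F-test on ranks as a check against outliers, with a note that it can drift slightly above 5% if centre differences are large. Keep M-estimation for the treatment-plus-centre model only.

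If the sponsor prefers a robust interaction test, the SAP should name the weight function, scale and test statistic, and calibrate the p-value by permutation or bootstrap.

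The cost is one SAP sentence and one standard ANOVA run, settled before unblinding. No extra data or subjects are needed, and the SAP again agrees with the protocol on this test.
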